9.7.1.6.1 PRIMARY EFFICACY ANALYSIS

The primary analysis will be based on an intent to treat philosophy without regard to adherence to treatment. The primary analysis of the change from baseline in CDR-SB at 24 months will be performed to compare elenbecestat (E2609) 50 mg per day versus placebo using a linear mixed effects model for repeated measures (MMRM) on the FAS. The MMRM model will include baseline CDR-SB as a covariate, with treatment group, visit, randomization stratification variables (ie, region [7 levels], clinical dementia [yes, no], and concurrent AD medication use at randomization (Visit 2) [yes, no]), and treatment group-by-visit interaction as fixed effects. (revised per Amendments 01 and 02) An unstructured covariance matrix will be employed to model the covariance of within subject effect; if MMRM fails to converge then a covariance structure with fewer parameters from the following list will be employed according to the prespecified order in the list until the MMRM converges. The list of covariance structure will include Heterogeneous Toeplitz, Toeplitz, Heterogeneous Compound Symmetry, and Compound Symmetry. This primary analysis will include all observed post baseline data of the change from baseline in CDR-SB without imputation of missing values. The treatment effect for elenbecestat (E2609) versus placebo will be compared at 24 months based on MMRM model. The LS means and difference in LS means between elenbecestat (E2609) treatment group and placebo, and corresponding 95% CI will be presented.

The null hypothesis is that there is no difference in the mean change from baseline in CDR-SB at 24 months between elenbecestat (E2609) 50 mg per day and placebo. The corresponding alternative hypothesis is that there is a difference in the mean change from baseline in CDR-SB at 24 months between elenbecestat (E2609) 50 mg per day and placebo.

The primary analysis will be repeated to minimize the impact of change in concomitant AD medications where efficacy data after initiation of new AD medications and increase of current AD medications will be censored.

The following sensitivity analysis will be conducted to evaluate the impact of missing data: the primary endpoint will be analyzed using ANCOVA after multiple imputation. The ANCOVA model will include baseline CDR-SB as a covariate, with treatment group and randomization stratification variables as factors.

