9.7.2 Determination of Sample Size

The sample size for this study is estimated based on comparison of elenbecestat (E2609) versus placebo with respect to the primary efficacy endpoint, the change from baseline CDR-SB at 24 months. Based on available ADNI data [amyloid positive, MMSE equal or greater than 24, late MCI (global CDR=0.5) populations from ADNI, ADNI 2 and ADNI GO] the mean and the standard deviation of the change from baseline in the CDR-SB at 24 months in the placebo group are assumed to be 1.75 and 2.05, respectively. Therefore, assuming a 25% reduction in the mean change from baseline CDR-SB at 24 months for the elenbecestat (E2609) 50 mg per day dose group compared to placebo with a common standard deviation of 2.05 and an estimated 30% dropout rate in this study, a total sample size of 1330 subjects, 665 subjects in each treatment group, will be required to detect the treatment difference between elenbecestat (E2609) 50 mg per day and placebo using a 2-sample t-test with 90% power at a significance level of 2-sided alpha =0.05.

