9 INVESTIGATIONAL PLAN

9.1 Overall Study Design and Plan

This study is a 24-month treatment, multicenter, double-blind, placebo-controlled, parallel-group study in EAD including MCI due to AD (Albert, et al., 2011) and the early stages of mild AD. In addition, the MCI due to AD population will also be consistent with the research criterion for “Prodromal AD” (Dubois, et al., 2010) in that episodic memory will be impaired on a list learning task (ISLT). An open-label Extension Phase will be available for subjects who complete the full 24 months of treatment in the Core study. The Extension Phase will continue until commercial availability of elenbecestat (E2609), or until a positive risk-benefit assessment in this indication is not demonstrated. Full details of the Extension Phase will be available in a future protocol amendment. A total of 1330 subjects will be randomized, in a double-blind manner, to receive either placebo or elenbecestat (E2609) 50 mg per day (approximately 1:1 randomization ratio) for 24 months. Randomization will be stratified according to region (7 levels), clinical dementia staging with no more than approximately 25% of the randomized subjects diagnosed with the early stages of mild dementia due to AD, and concurrent AD medication use. The 7 levels of region are: (revised per Amendment 02)

1. North America
2. Western Europe (including Oceania region)
3. Eastern Europe
4. Japan
5. China
6. Other Asian countries
7. South America

(revised per Amendments 01 and 02)

The study is designed to have more frequent visits focused on safety assessments during the first 3 months of treatment.

Two longitudinal biomarker substudies will evaluate the effects of study treatment on the underlying pathophysiology of AD using amyloid PET and/or CSF biomarkers. Participation in the substudies is optional and will require specific consent that will not affect enrollment or treatment in the main study.

The maximum estimated duration for each subject on study is approximately 29 months (ie, 2-month Prerandomization Phase, followed by 24 months of treatment and a 3-month Follow-Up Phase).

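### The fallback list for the primary MMRM contains two equal-variance structures, one tried before Heterogeneous Compound Symmetry; if one is reached with model-based standard errors and growing variance, the month-24 test is anti-conservative

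*Protocol*

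**What the plan says.** Section 9.7.1.6.1 makes unstructured the first choice for the within-subject covariance. If the model does not converge, "a covariance structure with fewer parameters from the following list will be employed according to the prespecified order", until one converges. The list reads: "The list of covariance structure will include Heterogeneous Toeplitz, Toeplitz, Heterogeneous Compound Symmetry, and Compound Symmetry". The section promises LS means, their difference and a 95% CI. It does not say whether standard errors are model-based or empirical, for the unstructured fit or for a fallback.

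The CDR is rated every 3 months (Section 9.1.2.1 and Table 3), which gives 8 post-baseline visits from month 3 to month 24. The test is at month 24 alone. Section 9.7.1.6.2 applies the same MMRM to the other continuous secondary endpoints and analyses the CDR-SB slope with a random coefficient model. Section 9.7.2 gives an SD for month 24 only: the mean and SD of the change "in the placebo group are assumed to be 1.75 and 2.05, respectively".

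**The concern.** A prespecified fallback is meant to keep the confirmatory test valid when the first model fails. Toeplitz and Compound Symmetry estimate a single variance pooled over all visits. If subjects decline at different rates, the spread of change from baseline widens with time. The pooled variance then falls below the month-24 variance, and a model-based standard error for the month-24 contrast is too small.

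The protocol does not state early-visit SDs, so growth is an assumption. It agrees with the protocol's own random coefficient model, in which subject-specific slopes make variance rise with time. The assumed month-24 SD (2.05) also exceeds the assumed mean change (1.75), which suggests that progression differs widely between subjects.

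The order adds to the problem. The first structure to converge is used, so Toeplitz would be adopted before Heterogeneous Compound Symmetry, which keeps a separate variance for each visit.

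**Working it through.** **Inputs from the protocol.** Month-24 SD 2.05; effect 0.25 × 1.75 = 0.4375 points ("assuming a 25% reduction in the mean change from baseline CDR-SB at 24 months"); "an estimated 30% dropout rate in this study"; "a total sample size of 1330 subjects, 665 subjects in each treatment group"; 8 post-baseline visits.

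**The plan's own figure.** n per arm = 2 × (1.960 + 1.282)² × 2.05² / 0.4375², which rounds up to 462 (463 with the t distribution). Dividing by 0.70 gives 660 (662) per arm, or 1320 to 1324 in total, against the stated 1330. Power with 465 completers per arm (0.70 × 665) is 0.902. The stated size is reproduced.

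**Covariance parameters with 8 visits.** Unstructured 8 × 9 / 2 = 36; Heterogeneous Toeplitz 8 + 7 = 15; Toeplitz 8; Heterogeneous Compound Symmetry 8 + 1 = 9; Compound Symmetry 2.

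**Assumptions.** Model-based standard errors; month-3 SD from 0.8 to 2.05 (2.05 means no growth); true correlation autoregressive-type, constant, or from random slopes; dropout 0% or 30%, unrelated to outcome and equal by arm.

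**Formula.** Type I error = 2 × [1 − Φ(1.96 × r)], where r is the model-based standard error of the month-24 contrast divided by its true standard error.

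**Hand check: Compound Symmetry, complete data, random slopes, month-3 SD 1.0.**
- Variance at month t is a + c·t². From the two SDs, c = (4.2025 − 1) / (576 − 9) = 0.005648 and a = 1 − 9c = 0.949.
- The mean of t² over months 3, 6, …, 24 is 9 × 204 / 8 = 229.5.
- Pooled variance = 0.949 + 0.005648 × 229.5 = 2.245, against 4.2025 at month 24.
- r = √(2.245 / 4.2025) = 0.731. Type I error = 2 × [1 − Φ(1.433)] = 15.2%.

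**Results over the assumed range.**

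| Month-3 SD | Toeplitz | Compound Symmetry |
|---|---|---|
| 2.05 (no growth) | 5.0% | 5.0–6.4% |
| 1.5 | 7.8–9.7% | 7.7–10.5% |
| 1.0 | 11–15% | 11–18% |
| 0.8 | 13–17% | 13–21% |

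**The heterogeneous structures, same range.** Heterogeneous Toeplitz gives 5.0% when the true correlation depends only on the lag between visits, and 6–10% under random slopes, where it does not. Heterogeneous Compound Symmetry gives 4–7%.

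**Steeper growth.** Random-slope or Brownian-type truths with error SD 0.3 to 0.8 and 30% dropout give about 9–18% for Toeplitz, 11–26% for Compound Symmetry, 8–14% for Heterogeneous Toeplitz and 5–7% for Heterogeneous Compound Symmetry. The steepest case is extreme: with random slopes and error SD 0.3, the month-3 variance is 0.09 + (4.2025 − 0.09) / 64 = 0.154, an SD of 0.39.

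**Monte Carlo check.** 6000 runs, 465 per arm, complete data. A pooled variance gives 5.1%, 7.6%, 11.6% and 13.8% for month-3 SD 2.05, 1.5, 1.0 and 0.8. A visit-specific variance gives 4.98% to 5.05%.

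**The case against.** - **The estimator may be settled elsewhere.** The protocol names none, and the choice is commonly left to the SAP, which is not shown. A reader might infer that the plan uses model-based standard errors; it does not say so. With an empirical variance the understatement disappears. This stands, so the inflation is conditional.
- **Not every fallback is poor.** A reader might infer that any fallback pushes type I error far above 5%. That does not follow. Heterogeneous Toeplitz, tried first, holds 5% under a lag-dependent correlation, and Heterogeneous Compound Symmetry stays near nominal. Reaching Toeplitz requires both unstructured and Heterogeneous Toeplitz to fail.
- **The trigger is remote.** Thirty-six covariance parameters are few for 1330 subjects. As an illustration only, a path with 16% error, reached 1% of the time independently of the data, would add 0.01 × (16 − 5) = 0.11 percentage points overall. This stands and limits the weight of the point.
- **The order contradicts nothing.** All four structures have fewer parameters than unstructured, and no decreasing order is promised. The objection to the order is that Toeplitz saves one parameter (8 against 9) at the price of the visit-specific variances.
- **There is a cross-check.** The prespecified ANCOVA after multiple imputation does not pool variance over visits. It would expose a discrepancy, so one cannot say that a fallback result could never be believed. It is a sensitivity analysis, however, and does not replace the primary test.

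**Conclusion.** The point holds in conditional form. The defect is in a rule the protocol states: two of the four fallbacks impose equal variances on a contrast at the last visit, and one of them precedes a safer structure. If one of these two is used with model-based standard errors and the variance grows, type I error is roughly 8 to 20%, and somewhat more under the steepest growth tried. With no growth it is about 5 to 6%. Heterogeneous Toeplitz ranges from 5% to about 14% and Heterogeneous Compound Symmetry from about 4 to 7%.

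These figures rest on early-visit SDs and a standard-error estimator that the protocol does not give, and on dropout unrelated to outcome. Because the path is unlikely to be taken at this sample size, the change is cheap protection for a contingency. It does not show that the planned primary analysis is invalid.

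**What to change.** In Section 9.7.1.6.1 and the matching synopsis text:
- Delete Toeplitz and Compound Symmetry from the list, or place both after Heterogeneous Compound Symmetry.
- State that any fit with a covariance other than unstructured uses the empirical (sandwich) variance for tests and confidence intervals. This also covers Heterogeneous Toeplitz.
- Apply the same rule to the secondary endpoints analysed by MMRM, which are tested in sequence at 0.05.

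The sandwich variance corrects the standard error. It does not remove bias in the estimate when the covariance is misspecified and dropout depends on earlier outcomes, which is a further reason to delete the equal-variance structures.

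The cost is one or two sentences. Nothing changes if the unstructured model converges, and with about 665 subjects per arm the small-sample penalty of the sandwich variance is negligible.

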9.7.1.6.2 SECONDARY EFFICACY ANALYSES

The secondary analyses will be performed only if the primary analysis is significant. The treatment effect for elenbecestat (E2609) 50 mg/day versus placebo, for each secondary efficacy endpoint, will be tested using a sequential testing procedure at a significance level of 2-sided $\alpha = 0.05$, ie, any test will start only if the test with higher hierarchical order is significant. The final hierarchical order will be specified later in the statistical analysis plan before database lock.

Time to worsening of CDR scores by 24 months will be analyzed on the FAS using Cox regression model for treatment effect adjusting for randomization stratification factors. Time to worsening of a CDR score is defined as time from randomization to worsening of the CDR score (ie, the first worsening in 2 consecutive scheduled visits). For subjects whose CDR scores have not worsened by the end of study, the time to worsening of the CDR score will be censored at the date of last CDR assessment for these subjects.

Time to conversion to dementia for subjects who were not clinically staged as dementia at Baseline based on clinical diagnosis will be analyzed on the FAS using Cox regression model for treatment effect adjusting for randomization stratification factors. Proportion of subjects with dementia diagnosis at 24 months will be estimated using Kaplan—Meier method based on time to conversion to dementia based on clinical diagnosis. Time to conversion to dementia for subjects who were not clinically staged as dementia at Baseline based on clinical diagnosis is defined as time from randomization to conversion to dementia based on clinical diagnosis. For subjects without clinical dementia by the end of study, the time to conversion to dementia based on clinical diagnosis will be censored at the date of last dementia diagnosis.

The rate of change over time (mean slope) based on change from baseline in the CDR-SB will be analyzed using linear mixed effects (LME) models for multivariate normal data derived from a random coefficient model (slope analysis), where the mean slope in each group depends on a continuous assessment time. The LME model will include baseline CDR-SB, randomization stratification variables, assessment time, and treatment group-by-assessment time.

The other continuous secondary efficacy endpoints as defined above will be analyzed using the same MMRM model as the primary efficacy analysis to compare elenbecestat (E2609) 50 mg per day versus placebo on the FAS, using baseline value corresponding to the response variable in the model.

The relationship between clinical changes at 24 months (CDR-SB, ADAS-cog₁₄, MMSE, and FAQ) and changes in each of the biomarkers (amyloid PET, CSF t-tau and p-tau, vMRI, and fMRI) at 24 months, will be evaluated using an ANCOVA model. (revised per Amendment 01) Changes in clinical scales at 24 months will be the response variables and either continuous or categorical change of biomarkers will be independent variables. The ANCOVA model will also include baseline value for clinical scale as a covariate,

randomization stratification variables, treatment group as factors, and other terms as appropriate.

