Abnormal ECG (QTc) results, if not otherwise considered part of a clinical symptom that is being reported as an AE, should be considered an AE if the QTc interval is more than 450 ms and there is an increase of more than 60 ms from baseline. If the QTcF is greater than 450 ms on the first single 12-lead ECG, 2 additional 12-lead ECGs will be performed 1 minute apart and the mean of the 3 QTcF values will be calculated. Any ECG abnormality that the investigator considers as an AE should be reported as such.

Cognitive decline will be assessed as a safety assessment in addition to an efficacy assessment. Cognitive assessments include the CDR, ADAS-cog₁₄, and MMSE (see [Section 9.5.1.3.1](#)). If these assessments show cognitive decline during the Treatment Period, and if this cognitive decline is considered by the investigator to be excessive relative to the subject's recent AD history, this finding should be reported as an AE. It is the responsibility of the investigator to review the cognitive assessments and to determine if any result constitutes an AE.

AEs that might indicate signals of possible drug abuse potential will require a more detailed follow-up through completion of a specific eCRF form. This includes AEs that fall into the following categories and examples of such AEs are provided in [Appendix 3](#).

- Euphoric mood
- Elevated mood
- Feeling abnormal
- Feeling drunk
- Feeling of relaxation
- Thinking abnormal
- Hallucination
- Inappropriate affect
- Mood disorders and disturbances
- Drug tolerance
- Psychosis
- Dissociative state

It is also the responsibility of the investigator to review the results of the C-SSRS/clinical assessment of suicidality in all subjects and determine if any result constitutes an AE. Medical and scientific judgment should be exercised in deciding whether an isolated

suicidality rating scale response should be classified as an AE (see [Section 9.5.1.5.9](#) for a description of the C-SSRS and of the clinical assessment of suicidality).

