9.7.1.1.2 SECONDARY ENDPOINTS

The secondary endpoints of the study are:

- Time to worsening of CDR scores by 24 months (eg, the worsening of global CDR score is defined as an increase from baseline by at least 0.5 points on the global CDR scale on 2 consecutive scheduled visits at which global CDR is undertaken)
- Time to conversion to dementia for subjects who were not clinically staged as dementia at Baseline based on clinical diagnosis
- The rate of change over time (mean slope) based on CDR-SB score over 24 months
- Change from baseline in CDR-SB at 27 months (ie, 24 months of treatment plus 3 months posttreatment follow-up) (revised per Amendment 01)
- Change from baseline in ADAS-cog₁₄, MMSE, and FAQ at 24 months
- Change from baseline in ADAS-cog₁₄ Word List (immediate recall and delayed recall) at 24 months (revised per Amendment 01)

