9.7.1.8 Safety Analyses

Evaluations of safety will be performed on the Safety Analysis Set. The incidence of AEs, out-of-normal-range laboratory safety test variables, abnormal ECG findings, and out-of-range vital signs, suicidality, results of the sleep questionnaire, along with change from baseline in laboratory safety test variables, ECGs, and vital sign measurements will be summarized by treatment group. (revised per Amendment 01)

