9.7.1.8.5 OTHER SAFETY ANALYSES

Cognitive decline will be assessed as a safety assessment, in addition to efficacy assessments. Cognitive assessments will include the ADAS-cog₁₄, MMSE, and CDR. (see [Section 9.7.1.6](#)).

vMRI will be used to evaluate disease modification as indicated by measurements of brain atrophy, including the change from Baseline in terms of the measured hippocampal volume based upon the centralized measurement of the structure on repeated MRIs. A large number of studies, including the AD Neuroimaging Initiative, have shown that quantitative measurements of hippocampal, whole brain, and total ventricular volume provide robust and reliable biomarkers of disease progression, and potential for assessment of PD efficacy.

MRI sequences will be collected for all subjects at 12 and 24 months per the Schedule of Assessments. vMRI data will be analyzed at the Screening Visit and at Visits 9 and 13 (12 and 24 months of treatment). QC and normalization procedures for measurements of the whole brain, total ventricular volume, and right and left hippocampal volumes will be based on a validated algorithm and conducted in the same central laboratory. Additional analysis of regions of interest and cortical thickness may also be performed.

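### The protocol makes running the secondary analyses, not only claiming from them, depend on a significant primary, so after a null or modestly adverse CDR-SB result no between-arm estimate of ADAS-cog14 or MMSE is provided for, although the safety section relies on them

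*Protocol*

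**What the plan says.** Section 9.7.1.6.2 opens with the rule "The secondary analyses will be performed only if the primary analysis is significant". It then restricts testing separately through a fixed sequence: "any test will start only if the test with higher hierarchical order is significant". The order of the sequence is left to the SAP; the opening rule is not. The same rule stands under Analyses for Secondary Efficacy Endpoints in the synopsis and in each version of Section 9.7.1.6.2 in the file.

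Section 9.7.1.1.2 lists among the secondary endpoints "Change from baseline in ADAS-cog₁₄, MMSE, and FAQ at 24 months". Their between-arm model is given inside the conditional section: "The other continuous secondary efficacy endpoints as defined above will be analyzed using the same MMRM model as the primary efficacy analysis". Time to worsening of CDR, time to conversion to dementia, the CDR-SB slope and the ANCOVA relating clinical to biomarker change are described there too.

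On safety, Section 9.7.1.8.5 says "Cognitive decline will be assessed as a safety assessment, in addition to efficacy assessments" and "Cognitive assessments will include the ADAS-cog₁₄, MMSE, and CDR", with a cross-reference to Section 9.7.1.6. Section 9.5.1.5.1 says much the same: "Cognitive decline will be assessed as a safety assessment in addition to an efficacy assessment". The list of safety summaries in Section 9.7.1.8 names no cognitive scale; after adverse events and laboratory tests it continues with "abnormal ECG findings, and out-of-range vital signs, suicidality, results of the sleep questionnaire, along with change from baseline in laboratory safety test variables".

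**The concern.** A gatekeeping rule is there to control which results may be claimed. It need not stop anyone from estimating the others. Here the operative word is *performed*, and because the next sentence already limits testing, the opening rule reads as an additional bar on running the analyses at all.

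That conflicts with Section 9.7.1.8.5, which counts ADAS-cog14 and MMSE among three cognitive safety measures and relies on Section 9.7.1.6 for their analysis. When the primary is not significant, the only between-arm model described for those two scales falls away. A null or slightly adverse CDR-SB result is when a reader would most want to see them.

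The ranking is also odd. Section 9.7.1.6.3 compares NPI-10, EQ-5D, QOL-AD and Zarit's Burden Interview by arm with no such condition, and Section 9.7.1.7.3 places the biomarker comparisons outside sequential testing. After a failed primary, caregiver burden would be compared between arms while ADAS-cog14, MMSE and FAQ would not.

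**Working it through.** **Which analyses survive a non-significant primary, read literally**

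| Measure | Where analysed by arm | Conditional on the primary? |
|---|---|---|
| CDR-SB at 24 months | 9.7.1.6.1 (LS means, difference, 95% CI) | No |
| ADAS-cog14, MMSE, FAQ | 9.7.1.6.2 | Yes |
| Conversion to dementia, CDR-SB slope | 9.7.1.6.2 | Yes |
| Clinical-biomarker relationships (not a between-arm estimate) | 9.7.1.6.2 | Yes |
| NPI-10, EQ-5D, QOL-AD, Zarit | 9.7.1.6.3 | No |
| Biomarkers | 9.7.1.7.3 | No |
| Treatment-emergent adverse events | 9.7.1.8.2 | No |

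**How often the condition fails**

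Inputs from Section 9.7.2: placebo change 1.75, SD 2.05, 25% reduction, 30% dropout, 665 per arm, two-sided alpha 0.05, 90% power.

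1. Reproduce the plan's figure. The design difference is 0.25 × 1.75 = 0.4375. Then n per arm = 2 × (1.960 + 1.282)² × 2.05² / 0.4375², which rounds up to 462. Allowing for dropout, 462 / 0.70 = 660 per arm, or 1320 in total, against the stated 665 and 1330 (0.8% apart). The plan's figure reproduces.
2. Evaluable per arm: 665 × 0.70 = 465.5. SE of the difference = 2.05 × √(2 / 465.5) = 0.1344. Power at 0.4375 is 90.2%.
3. The observed difference must exceed 1.960 × 0.1344 = 0.263 points, in either direction, for the primary to be significant.
4. For a true difference d, P(significant) = 1 − Φ(1.960 − d/SE) + Φ(−1.960 − d/SE).

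| True CDR-SB difference (drug worse) | Primary significant | Primary not significant |
|---|---|---|
| 0 | 5.0% | 95.0% |
| 0.1 | 11.5% | 88.5% |
| 0.2 | 31.9% | 68.1% |
| 0.3 | 60.7% | 39.3% |
| 0.4375 | 90.2% | 9.8% |

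The harm sizes are assumptions; the protocol gives none. The formula is symmetric, so the last row applies equally to a benefit of the planned size: about one trial in ten would miss significance and, read literally, run no secondary analyses.

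These figures give the chance that the condition fails on CDR-SB. They are not the chance that harm on ADAS-cog14 or MMSE goes unseen, for which the protocol supplies no variance or effect size.

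**The case against.** A reader might infer that a drug which fails or does harm leaves cognitive safety unanalysed. The documents do not support that, for three reasons.

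- CDR is itself one of the three named cognitive safety measures, and CDR-SB is always analysed with LS means, a difference and a 95% CI. The half-width is about 0.263 points, or 0.263 / 1.75 = 15% of the assumed placebo change, so even a non-significant result bounds harm on that scale.
- Section 9.5.1.5.1 has decline on CDR, ADAS-cog14 or MMSE reported as an adverse event when the investigator judges it excessive. Section 9.7.1.8.2 tabulates treatment-emergent events by arm unconditionally, and the DSMB reviews safety data throughout.
- The primary hypothesis is two-sided. Harm as large as the design effect would make the primary significant about 90% of the time and so satisfy the opening rule.

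All three stand, and they lower the weight of the point. They do not replace the missing estimates. Section 9.2.1 notes that CDR-SB does not rest directly on psychometric tests, whereas ADAS-cog14 and MMSE are such tests. The adverse-event route depends on judging individual decline in a population expected to worsen, so a modest shift in the mean could pass unnoticed.

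It can also be argued that the rule, placed under secondary efficacy, governs efficacy testing only and that Section 9.7.1.8.5 is a separate duty. That is a reasonable reading of intent, but the text does not say so, and the cross-reference leads into the section containing the condition.

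Finally, that Section 9.7.1.8.5 sets out no method of its own is detail a protocol may leave to the SAP. It is not part of this point.

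**Conclusion.** The rule as written is wrong in a limited way. Followed literally, a null or modestly adverse CDR-SB result leaves no between-arm estimate of ADAS-cog14, MMSE, FAQ, time to conversion to dementia or the CDR-SB slope, and no analysis of the clinical-biomarker relationships. This contradicts the reliance on ADAS-cog14 and MMSE in Section 9.7.1.8.5. Under SD 2.05, 465.5 evaluable per arm and a two-sided 5% test, the condition fails in about 95% of trials with no effect, 68% at 0.2 points worse and 39% at 0.3 points worse.

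The point covers null or modest results on CDR-SB and harm confined to ADAS-cog14 or MMSE. It does not extend to clear harm on CDR-SB, and it leaves the primary result untouched. Severity is moderate.

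**What to change.** In Section 9.7.1.6.2 replace the opening rule with wording such as:

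> Confirmatory testing of secondary endpoints proceeds only if the primary is significant and follows the fixed sequence. Estimates and 95% CIs by arm for all secondary endpoints are reported whatever the primary result, labelled nominal below the break.

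Mirror this in the synopsis. In Section 9.7.1.8.5 add one sentence stating that the by-arm comparisons of ADAS-cog14, MMSE and CDR do not depend on the primary result.

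The cost is a sentence or two in each place. The data are collected and the models planned already. Estimates reported outside the confirmatory sequence spend no alpha, so the sample size of 1330, the power of about 90% and the type I error are unchanged.
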